#### 8.2 Reporting of Adverse Events

#### • Diagnoses vs. Signs/Symptoms

Each AE should be recorded to represent a single diagnosis. Accompanying signs (including abnormal laboratory values if not constituting AEs themselves) or symptoms should NOT be recorded as additional AEs. If a diagnosis is unknown, sign(s) or symptom(s) should be recorded as an AE.

#### Laboratory Values

Changes in laboratory values may be considered AEs if they are judged to be clinically significant (i.e., if some action or intervention is required or if the Investigator judges the change to be beyond the range of normal physiological fluctuation). If abnormal laboratory values are the result of pathology for which there is an overall diagnosis (e.g., increased creatinine in renal failure), the diagnosis only should be reported as an AE.

#### • Pre-existing Conditions

Pre-existing conditions (present before the start of the AE collection period) are considered concurrent medical conditions and should NOT be recorded as AEs. However, if the subject experiences a worsening or complication of such a concurrent condition, the worsening or complication should be recorded as an AE. Investigators should ensure that the AE term recorded captures the change in the condition (e.g., "worsening of....").

#### • Preplanned Surgeries or Procedures

Preplanned procedures (surgeries or therapies) that were scheduled prior to the start of an AE are not considered AEs. However, if a preplanned procedure is performed early (e.g., as an emergency) due to a worsening of the preexisting condition, the worsening of the condition should be captured as an AE.

#### • Elective surgeries or procedures

Elective procedures performed where there is no change in the subject's medical condition should not be recorded as AEs, but should be documented in the subject's source documents.

## • Overdose

Cases of drug overdose without manifested side effects are NOT considered AEs.

#### 8.3 Assessment of Adverse Event Severity

The following guidelines for rating severity of adverse events should be used.

#### Mild:

Awareness of signs or symptoms, but easily tolerated; are of minor irritant type; no loss of time from normal activities; symptoms would not require medication or a medical evaluation; signs and symptoms may be transient, disappearing during continued treatment with study medication.

#### Moderate:

Discomfort enough to cause interference with usual activities; the study medication may have been interrupted.

#### Severe:

Incapacitating with inability to do work or do usual activities; signs and symptoms may be of systemic nature or require medical evaluation; the study drug may have been stopped, and treatment for the event may be required.

The term "severe" is often used to describe the intensity of a specific event, as in mild, moderate or severe myocardial infarction; the event itself however, may be of relatively minor medical significance, such as severe headache. This is not the same as serious, which is based on subject/event outcome or action criteria usually associated with events that pose a threat to a subject's life or functioning. The Investigator must decide whether each AE meets the definition of an SAE.

## 8.4 Serious Adverse Events

An SAE is any untoward medical occurrence that:

- Results in death.
- Is life-threatening. Life-threatening, in the definition of serious, refers to an event in which the subject was at risk of death at the time of the event; it does not refer to an event which hypothetically might have caused death if it were more severe.
- Requires hospitalization (> 24 hours) or prolongation of existing hospitalization.
- Results in persistent or significant disability/incapacity.
- Is a congenital anomaly/birth defect.

BHR-700 (0.2% 4-Hydroxytamoxifen (4-OHT) Gel) BHR PHARMA, LLC

[figure not shown]
• Is considered medically significant by the Investigator or requires intervention to prevent any one of the outcomes above. Medically significant are those events considered important in the Investigator's opinion that may not be immediately life-threatening or result in death or hospitalization but may jeopardize the subject or may require intervention to prevent one of the other outcomes listed in the definition above. These will also usually be considered serious.

All SAEs will be captured for the duration of the study. The reporting period begins with the first dose of study drug (Study Day 1) and ends at Week 52 and Week 104. All SAEs should be monitored until they are resolved or are clearly determined to be due to a subject's stable or chronic condition or intermittent illness.

Cause of death is required whenever known. If an autopsy was performed, an autopsy report should be provided. Death should usually be reported as the outcome of a specific SAE. Reports for hospitalization of elective procedures do not need to be reported as SAEs if there are no precipitating signs/symptoms or worsening of a pre-existing condition that necessitated the procedure. However, SAEs must be reported for any complications resulting from a procedure that prolonged the hospitalization.

## • SAE Reporting

The SAE Form should be completed *within 24 hours of the Investigator/Site learning of the event* and sent as a PDF by email to a secure safety email box. On receipt, the SAE form will be disseminated to:

For each SAE, the Investigator and Sponsor will independently assess whether there is a reasonable possibility that the event may have been caused by the study drug ("drug-related"). The Sponsor will evaluate each drug-related SAE to determine if the event was unexpected. If the SAE is assessed to be both drug-related and unexpected, the Sponsor or designee will notify all Investigators, and will report it to the appropriate regulatory authorities as required by applicable local regulations. The Sponsor or designee will report SAEs, including narratives, to the U.S. FDA and local regulatory authorities as required by 21 CFR 312.32 and the International Conference on Harmonisation (ICH) Guideline for Good Clinical Practice. The Investigator is responsible for notifying his/her respective IRB.

## 8.5 Laboratory Tests

Laboratory tests (hematology and blood chemistry) will be performed by a central laboratory. Laboratory tests will be performed at screening, at pre-dose, at Week 26 and Week 52. For those subjects who have elected to continue open-label treatment for a further 52 weeks, laboratory tests will also be performed at Week 78 and Week 104. The Investigator will assess all abnormal lab values for clinical significance; if categorized as AEs, they will be collected and recorded similarly to other AEs. All clinically significant abnormal lab values will be followed until resolution. If resolution is not seen, a justification as to the cause for such an abnormality, such as due to an underlying pre-existing condition, associated co-morbidity, etc., will be recorded.

The following laboratory assessments will be performed for this study: Hematology, Blood Chemistry, Coagulation factors, Hormones, and Bone biomarkers.

Any residual biological samples will be destroyed after test results are confirmed by the respective testing laboratory. No samples will be retained for future testing.

#### 8.6 Physical Examination

A Physical Examination (PE) including a breast exam will be performed at screening, pre-dose on Day 1 (only if the subject has reported any changes since the Screening Visit), and Week 52. For those subjects who have elected to continue open-label treatment for a further 52 weeks, a PE will also be performed at Week 104. A breast exam and mammogram will be performed at Week 104 for those subjects who have elected to continue open-label treatment for a further 52 weeks. Any significant findings present prior to the first dose of study drug (Study Day 1) must be reported on the PE CRF. Significant findings made after the first dose of study drug which meet the definition of an AE must be recorded on the AE CRF. The PE will include an assessment of all body systems.

## 8.7 Vital Signs

The measurement of Vital Signs and weight will be made at screening, pre-dose and at weeks 13, 26, 39, and 52. For those subjects who have elected to continue open-label treatment for a further 52 weeks, Vital Signs will also be performed at weeks 65, 78, 91, and 104. Any significant findings present prior to the first dose of study drug (Study Day 1) must be reported on the Vital Signs CRF. Sitting vital signs to be measured are: heart rate (beats/minute), respiration rate (breaths/minute), systolic and diastolic blood pressure (mmHg), and body temperature. Height will also be measured at pre-dose, week 52 and week 104 for those who elect to continue open-label treatment

#### 8.8 Mammogram

A bilateral mammogram with both the raw and processed 2D image DICOM files needs to be performed within 3 months prior to randomization. The same (make/model/serial number) mammography machine must be used for the Week 52 and if the subject is participating in the Open-Label phase, the Week 104 mammogram. If the mammogram is older than 3 months but less than 18 months, or it cannot be provided in the format required for the study, the mammogram can be repeated to meet the study entry requirement after informed consent has been obtained. Assuming the original mammogram has been made within 3 months before the date of randomization, the BI-RADS classification of this original mammogram will be used to assess and demonstrate the eligibility of the subject on inclusion criterion 1, a BI-RADS assessment C or D. The repeat mammogram will be used for determining the baseline density measurements, but not for re-assessment and/or confirmation of the BI-RADS criterion.

The mammography report must also be obtained. The breast density classification of C (heterogeneously dense) or D (extremely dense) should be recorded in the subject's study chart.

## 9.0 STATISTICAL ANALYSIS

#### 9.1 Statistical Analysis Plan

A statistical analysis plan (SAP) will be written and finalized prior to any lock of the study database. The SAP will give a detailed description of the summaries and statistical methodologies for analyses that will be performed and clearly describe when these analyses will take place. Should any inconsistencies exist between the analyses described in this section and the analyses described in the more detailed SAP, the SAP will take precedence.

#### **Blinded Treatment Phase**

#### **Primary Outcome Measure:**

• A comparison of reduction in breast density between BHR-700 gel and placebo treatment groups at 52 weeks using the Cumulus method.

#### **Secondary Outcome Measures:**

- Comparison of the reduction in breast density as calculated with the Volpara method and the Cumulus method.
- Laboratory parameters will be summarized in a descriptive fashion.
- Incidence and severity of AEs will be compared between BHR-700 gel and placebo.

#### **Open-Label Treatment Phase**

#### **Secondary Outcome Measures:**

- Comparison of the reduction in breast density as calculated with the Volpara method and the Cumulus method.
- Laboratory parameters will be summarized in a descriptive fashion.
- Incidence and severity of AEs will be compared between BHR-700 gel and placebo.

## 9.2 Sample Size

Assuming a reduction from baseline of 6% on active and 2% on placebo, with a common standard deviation of 8%, a total of 272 subjects will achieve a power of 90%, using a two sample, two-sided t-test at a significance level of < 0.01. Considering an attrition rate of 15%, 330 subjects are planned for enrollment in this study.

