# Table 1. ACR BI-RADS[©] Breast Tissue Composition

Approximately 330 subjects will be enrolled at approximately 25 sites located in the U.S. and Europe. Subjects who give informed consent will have screening evaluations, including hormone assessments of FSH, Estradiol, Estrone and LH to determine menopausal state. Those subjects meeting entry criteria, will be stratified, based on their hormone levels into either pre/peri or post-menopausal groups and randomized 2:1 within those groups to receive either 8 mg/day (4 mg/breast) 4-OHT or matching placebo for up to 52 weeks.

Subjects will apply the investigational gel to both breasts once per day. The first dose will be applied under the supervision of the Principal Investigator (PI) or designee. Subsequent doses will be self-administered at approximately the same time daily, after showering, by the subject until she has completed 52 weeks of study drug administration. There will be, in addition, an optional 52 weeks of open-label treatment for those subjects who choose to continue treatment. Subjects will capture daily gel administration in a diary to monitor compliance.

While on treatment, subjects will return to the clinic for study assessments, a review of AEs and to re-supply study gel at 13, 26, 39, weeks and at 52 weeks for those subjects who have agreed to take part in the open-label phase of the study. A schedule of study assessments is shown in Appendix 1.

During the study, in a case of significant changes in bleeding pattern or other signs/symptoms which could be related to endometrial pathology, the Investigator will perform a uterine ultrasound followed by an endometrial biopsy if indicated.

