#### 1.2 Design

This is a multi-center, randomized, double-blind, placebo-controlled study in women identified as having dense breast tissue upon screening mammography.

Subjects who give informed consent will have screening evaluations, including hormone measures of FSH, Estradiol and Estrone to determine menopausal state. Those subjects meeting entry criteria, will be stratified, based on their hormone levels, into pre/peri and post menopause groups and randomized within those groups 2:1 to receive either 8 mg/day (4 mg/breast) BHR-700 gel or placebo for up to 52 weeks. At the Principal Investigator's (PI) discretion, subjects may be allowed to reduce the dose to 4 mg/day (2 mg/breast) in cases of intolerance.

Subjects will apply the gel to both breasts once per day. The first dose will be applied under the supervision of the PI/designee. Subsequent doses will be self-administered daily by the subject until she has completed 52 weeks of study drug administration. Study drug compliance will be checked at each study visit. Subjects will be asked to capture daily gel administration in a diary and drug canisters will be weighed on release to the subject and on return. The canister weight will be recorded in grams. If the study drug is discontinued or interrupted, the reason(s) will be recorded. During treatment period, subjects will be evaluated at Day 1 and every 13 weeks (±2 weeks) thereafter.

A planned sample size of 330 women, identified as having dense breast tissue upon screening mammography, will be randomized to receive either BHR-700 gel or placebo (at 2:1 ratio). Considering an attrition rate of approximately 15%, it is expected to have 272 evaluable women (4-OHT: 181 & Placebo: 91) who will have both baseline and 52 week measurements of percent mammographic density (MD) of the breast.

Subjects who complete the double-blind phase of the study will be offered entry into an open-label follow-up period for an additional 52 weeks.

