# 2.3 Sample Size

Assuming a reduction from baseline in breast density of 6% on active and 2% on placebo, with a common standard deviation of 8%, a sample size of 272 subjects will achieve a power of 90%, using a two sample, two-sided t-test at a significance level of < 0.01. Considering an attrition rate of 15%, 330 subjects are planned for enrollment in this study.

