# 3. STATISTICAL METHODS

#### 3.1 General

All data will be analyzed using the Statistical Analysis System (SAS®; Version 9.2 or higher).

Safety and efficacy data will be summarized and presented by treatment group and time point in summary tables. Continuous variables will be presented by descriptive statistics: n, mean, standard deviation, median, minimum, and maximum. Categorical variables will be tabulated by frequency count and percentage.

When the actual treatment received by a subject is different from the randomized treatment assigned, the subject will be analyzed per the randomized treatment for the efficacy parameters (using the ITT population); while the subject will be analyzed per actual treatment that was taken for the safety parameters (using the safety population).

Where appropriate, all statistical tests will be two-sided hypothesis tests performed at the 5% level of significance for main effects and all confidence intervals will be two-sided 95% confidence intervals.

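### No analysis model is given for the between-arm density comparison; adjusting for baseline density and the menopausal randomisation stratum would be a free improvement to any such analysis, ad hoc ones included

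*Protocol*

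**What the plan says.** **Test named.** Protocol 9.2 bases the sample size on a calculation "using a two sample, two-sided t-test". SAP 2.3 has the same basis: "using a two sample, two-sided t-test at a significance level of < 0.01". The protocol synopsis repeats the sentence in its statistical methods, under the primary outcome measure. No other test or model for density appears in either document. Protocol 9.1 and SAP 2.2.1 say only that the arms will be compared at 52 weeks.

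**Stratification.** Protocol 4.0 says that eligible women "will be stratified, based on their hormone levels into either pre/peri or post-menopausal groups and randomized 2:1 within those groups". SAP 1.2 agrees: "into pre/peri and post menopause groups and randomized within those groups 2:1". No analysis section mentions the stratum.

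**Baseline.** The protocol synopsis and SAP 1.2 define evaluable women as those with both a baseline and a 52-week density measurement. The primary endpoint (synopsis; SAP 2.2.1) is a percentage reduction relative to the baseline mammogram.

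**Which text governs.** Protocol 9.1 leaves detailed methodology to the SAP and gives it precedence. The SAP was written after early termination. It puts description ahead of testing (1.3), plans no efficacy analysis for the report (3.3.2), rules out imputation (3.4.2), and allows ad hoc mammographic analyses after database lock, reported separately (3.3.2, 3.8). It gives no method for them.

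**The concern.** When randomisation is stratified, between-stratum differences in outcome are balanced by design. An unadjusted comparison leaves them in the error term, so its standard error is too large to the extent that the stratum predicts density change. A change score has a related weakness. Unless change is unrelated to baseline, a chance imbalance in baseline density carries over into the observed treatment difference, and a baseline covariate removes it. Both variables are already in the database.

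Two things are at stake. One is precision, which is scarcer than planned because SAP 1.3 reports fewer women and shorter treatment after termination. The other is that a density analysis chosen after lock, once the data have been reviewed, would have no covariate set fixed beforehand. Someone looking for a method would find only the t-test in the power statement.

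**Working it through.** **Inputs from the documents.** Reduction of 6% on active and 2% on placebo, so a difference of 4; common SD 8; two-sided alpha 0.01; power 90%; 272 evaluable women (Protocol 9.2, SAP 2.3). Allocation 2:1, giving 181 and 91 (protocol synopsis, SAP 1.2).

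**Step 1: reproduce the plan's figure.**
- Standard error of the difference = 8 × √(1/181 + 1/91) = 1.028.
- Noncentrality = 4/1.028 = 3.89.
- Noncentral-t power at two-sided alpha 0.01 = 90.2%.
- Required total: 270 by the normal approximation, 273 by noncentral t in complete 2:1 triplets, against 272 stated.

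The stated figure reproduces. It rests on an unadjusted SD of 8.

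**Step 2: baseline covariate.** Assume that the endpoint is absolute change, that variances at baseline and Week 52 are equal, and that their correlation is r. The documents give no r. With common variance σ², the variance of change is 2σ²(1 − r), and the residual variance after regression on baseline is σ²(1 − r²). The ratio is (1 + r)/2, so the adjusted SD is 8 × √((1 + r)/2). Power at 181/91, alpha 0.01:

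| r (assumed) | Variance factor | SD | SE of difference | Power |
|---|---|---|---|---|
| unadjusted | 1 | 8.00 | 1.028 | 90.2% |
| 0.95 | 0.975 | 7.90 | 1.015 | 91.0% |
| 0.9 | 0.95 | 7.80 | 1.002 | 91.8% |
| 0.8 | 0.90 | 7.59 | 0.975 | 93.3% |
| 0.7 | 0.85 | 7.38 | 0.948 | 94.7% |

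In sample-size terms, about 258, 245 or 231 women would give 90% power at r = 0.9, 0.8 or 0.7.

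**Step 3: stratum term.** If mean change differs by d between strata and a proportion p of women is in one stratum, the stratum accounts for d²p(1 − p)/64 of the variance. With p = 0.5 (assumed) this is 0.4% at d = 1, 1.6% at d = 2 and 6.3% at d = 4. The documents give neither d nor p. These shares should not simply be added to Step 2, because baseline density and menopausal status may overlap.

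**Step 4: cost.** The two terms use 2 degrees of freedom. If they explain nothing, power at 181/91 stays at 90.2%; the loss is below 0.01 percentage point.

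**The case against.** **The t-test is a planning device.** It occurs only inside power statements. A reader might infer that the plan chose an inferior analysis method, and the synopsis encourages this by placing the sentence in its statistical methods. The documents do not support that: even there, the sentence says only what 272 women would achieve, and Protocol 9.1 leaves the method to the SAP. Powering on a t-test and analysing with covariates are compatible. What remains is that no model is stated.

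**Baseline is already used.** A reader might infer that baseline density is ignored. It is not, since the endpoint is a reduction from baseline. It is absent only as a covariate.

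**No planned test loses precision.** This stands. The SAP plans no efficacy analysis, its output list has density listings but no density table, and hypothesis testing is played down. The point bears on the comparison as designed and on whatever ad hoc analysis follows.

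**The size is assumed.** This also stands. The factor (1 + r)/2 does not apply if the percentage reduction is a relative change. The figures use 181/91, which SAP 1.3 indicates no longer describes the data. They use alpha 0.01, whereas SAP 3.1 says that, where appropriate, "all statistical tests will be two-sided hypothesis tests performed at the 5% level of significance for main effects"; at 5% the unadjusted power at 181/91 is already 97.2%, so less than 3 points could be gained. Nothing in the documents shows that the stratum predicts density change.

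**Pooled visits.** SAP 3.8 merges End of Study visits into the nominal Week 52, so treatment durations differ. Covariate adjustment does not cure that.

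**Conclusion.** The point holds as a free improvement, not as an error in the plan. Neither document states a model for the between-arm density comparison, and neither baseline as a covariate nor the randomisation stratum is included. The governing SAP leaves any density analysis to ad hoc work with no stated method.

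The gain cannot be derived from the documents. On the assumptions of absolute change, equal variances and r between 0.95 and 0.7, it is 0.8 to 4.5 percentage points of power at the planned 181/91 and alpha 0.01. Any stratum gain depends on an unknown difference in change between strata. The total may be near zero.

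A reader might also infer that the sample size is wrong. It is not: 272 reproduces, and planning on the unadjusted SD becomes slightly conservative if the analysis adjusts.

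**What to change.** In SAP 2.2.1 and 3.3.2, state that any between-arm comparison of density, by Cumulus or Volpara and ad hoc analyses included, uses a linear model with treatment, baseline density by the same method, and menopausal stratum as randomised (pre/peri versus post). Report the adjusted difference with its confidence interval, which also suits the descriptive emphasis of SAP 1.3. Keep the t-test as the sample-size basis; no change to the sample size is needed.

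The cost is a few lines of SAP text and two model terms already collected. No new data are required.
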